4.1.2 Pre-clinical and Clinical Trials

Vericiguat has been evaluated in approximately 65 preclinical studies and has been administered to over 500 healthy subjects in 19 completed Phase I studies with single- and multiple-dose administration and approximately 740 heart failure subjects in two Phase IIb studies which studied vericiguat in worsening chronic heart failure subjects with reduced ejection fraction (HFrEF) and with preserved ejection fraction (HFpEF), respectively.

Dose finding in subjects with HFrEF was studied in the Phase IIb SOCRATES-REDUCED study (NCT 0195162). In this 12-week comparison of 4 different dosing strategies with placebo, vericiguat in doses up to 10 mg daily was well tolerated with a clinically significant reduction in N-terminal pro-Brain Natriuretic Peptide (NT-proBNP) levels in the 10 mg target dose arm [11] [12].

4.2 Rationale

4.2.1 Rationale for the Trial and Selected Subject Population

The worsening of chronic HF in patients despite the use of standard-of-care therapy as indicated by the need for hospitalization or the use of IV diuretics (without hospitalization) is associated with increased morbidity and mortality.

Vericiguat, a sGC stimulator, was studied in a Phase IIb dose-finding study (SOCRATES-REDUCED in subjects with HFrEF [NCT0195162]). In this trial, the highest target dose group demonstrated a reduction in NT-proBNP compared to placebo when added to standard of care. These findings support the rationale for this Phase III clinical outcome trial in HFrEF: VICTORIA Trial.

The VICTORIA trial will evaluate the clinical efficacy of vericiguat on a background of HF standard therapy for subjects with HFrEF [3] [8] and will determine the clinical efficacy of

vericiguat in a pivotal Phase III trial in line with the available guidance on clinical investigation of medicinal products for the treatment of cardiac failure [13].

The primary endpoint of the study is the time-to first occurrence of the composite of CV death or HF hospitalization. This endpoint integrates the cause-specific components CV death and HF hospitalization and is the most frequently used primary endpoint in recent Phase III HFrEF trials. Subjects without a HF hospitalization or CV death at the time of analysis will be censored at the time of a non-CV death or time of last information available for subjects still alive at time of analysis.

A futility interim analysis to assess lack of efficacy is planned at the time when approximately 75% of the planned number of CV death events is observed. The futility analysis will be performed with both the primary endpoint and CV death, and early termination of the study will be considered for lack of efficacy on both the primary composite endpoint and CV death. Additionally, a formal interim efficacy analysis for efficacy is also planned at the time when the futility analysis is performed. Within the pre-specified interim efficacy analysis, the primary purpose is to consider early termination of the study in the presence of substantial impact on both the primary composite endpoint and CV death.

A double-blind, randomized trial design comparing MK-1242 (vericiguat) versus placebo, on a background standard of care, offers an unbiased evaluation of MK-1242 (vericiguat) as a treatment option for this patient population with worsening HF in an international trial.

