8.4.1 Efficacy Endpoints

Primary Endpoint

The primary endpoint of the study is the time to the first occurrence of the composite endpoint of CV death or HF hospitalizations. Subjects without a HF hospitalization or CV death at the time of analysis will be censored at time of non-CV death or time of last information available during the pre-specified follow-up period for subjects still alive at time of analysis. Only clinical events confirmed by CEC will be used to define the primary endpoint.

Secondary Endpoints

The secondary study endpoints are:

- Components of the primary composite endpoint:
 - Time to CV death
 - Time to first HF hospitalization
- Time to total HF hospitalizations (first and recurrent)
- Time to first occurrence of the composite of all-cause mortality or HF hospitalization
- Time to all-cause mortality

Exploratory Endpoints

The following endpoints will be considered outside of the testing procedure and considered as exploratory endpoints:

- Time to first HF event, defined as composite of HF hospitalization or urgent HF visit (not meeting the criteria for a HF hospitalization).
- Time to first CV hospitalization
- Total number of HF hospitalizations
- Change from baseline in health-related quality of life measures (KCCQ and EQ-5D)

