Kaplan-Meier estimates of the primary composite endpoint (95% confidence interval) survival curves will be presented for each treatment group. Hazard ratio, relative risk reduction and corresponding 95% confidence intervals will be estimated based on a Cox proportional hazards model stratified by the same factors as used for the primary efficacy analysis.

The number and proportion of subjects with a CV death or HF hospitalization event will be provided by treatment group. In addition, rates per 100 patient-years will be provided.

Analysis of Secondary Endpoints

Analogous to the analysis of the primary endpoint, the analysis of the secondary efficacy endpoints will be performed under the intention to treat principle. All subjects randomized will be included in the analysis. Subjects will be analyzed as randomized.

A one-sided stratified log-rank test similar to the one used for the primary efficacy endpoint will be used to test if the time to first HF hospitalization, time to CV death, time to all-cause mortality, and time to first occurrence of the composite of all-cause mortality or HF hospitalization is prolonged in the vericiguat treatment group compared to placebo.

The time-to total HF hospitalization will be tested with an Andersen-Gill model [14] to compare the vericiguat treatment group to placebo. The Anderson-Gill model is an extension of the Cox proportional hazards model, where the hazard for the kth event, i.e. including both first and recurrent, for a subject i at time t, is given by

$$h_{ik}(t) = h_0(t) \exp(\beta T x),$$

with $h_0(t)$ being the baseline hazard and x the vector of covariates for subject i.

Treatment group and the stratification factors used for randomization will be included in the model as fixed effects. Robust standard errors will be used to account for correlations of event times within a subject [15] [16].

The following null hypothesis will be compared with the alternative hypothesis:

$$H_0: \quad HR_{\text{Vericiguat/Placebo}} = 1$$

$$H_1: \quad HR_{\text{Vericiguat/Placebo}} < 1$$

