Superiority of MK-1242 (vericiguat) over placebo in prolonging the time to total HF hospitalization will be concluded, if the upper limit of the confidence interval of the hazard ratio is below 1 with the confidence level matching the nominal alpha level used for testing at the interim or final analysis. Estimates of treatment comparisons and effect size including 95% confidence intervals will be provided based on the fitted model.

In addition, time to total HF hospitalizations and CV death will be analyzed using the Wei, Lin, Weissfeld (WLW) method [17], and details will appear in the supplemental SAP.

Missing Data

Subjects who prematurely withdraw from study treatment will be followed for further data collection. As long as the subject does not withdraw consent for any further data collection, every effort will be made to collect at least data on the components of the primary endpoint up to the last safety phone call which occurs two weeks after the final study visit. Subjects are requested to attend the protocol specified study visits. If a subject does not attend the regular study visits, the investigator will contact the subject via telephone to collect at least data for the primary endpoint.

Due to this follow up approach, it is expected that the amount of missing data will be only minor, as most subjects will be followed up until trial termination.

For the primary analysis, subjects without any HF hospitalization or CV death event at the time of analysis will be censored at their last available information or the date of their non-CV death. The censoring mechanism is assumed to be non-informative.

Supportive analyses will be performed to assess the impact of a potential informative censoring and missing data, and details will be described in the supplemental statistical analysis plan.

Table 7 Primary Analysis Strategy for Efficacy Variables

Endpoint/Variable	Statistical Method [†]	Analysis Population	Missing Data Approach
Primary Hypothesis:			
Time to first occurrence of the composite endpoint of CV death or HF hospitalization	Stratified Log-Rank Test	ITT	Censored at the last available information
Secondary Endpoints:			
Time to the first occurrence of CV death	Stratified Log-Rank Test	ITT	Censored at last known alive date
Time to the first occurrence of HF hospitalization	Stratified Log-Rank Test	ITT	Censored at the last available information

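### The Kaplan-Meier display of the primary composite treats non-CV death as ordinary censoring, so one minus the curve, if read as absolute risk, is slightly too high in both arms; a cumulative-incidence curve should be added

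*Combined protocol and SAP*

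**What the plan says.** The rationale in section 4.2.1 gives the rule: "Subjects without a HF hospitalization or CV death at the time of analysis will be censored at the time of a non-CV death". The operative text is in section 8. Section 8.4.1 says that event-free subjects "will be censored at time of non-CV death or time of last information available during the pre-specified follow-up period", and section 8.6.1 repeats this under the primary analysis and again under Missing Data, where it adds: "The censoring mechanism is assumed to be non-informative".

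For the display, section 8.6.1 says: "Kaplan-Meier estimates of the primary composite endpoint (95% confidence interval) survival curves will be presented for each treatment group". Two other absolute summaries follow: "The number and proportion of subjects with a CV death or HF hospitalization event will be provided by treatment group", and "In addition, rates per 100 patient-years will be provided". Inference rests on the stratified log-rank test and a stratified Cox model.

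The Missing Data text also promises that "Supportive analyses will be performed to assess the impact of a potential informative censoring and missing data", with details left to the supplemental SAP. One secondary endpoint in section 8.4.1 counts death from any cause: "Time to first occurrence of the composite of all-cause mortality or HF hospitalization".

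Neither a cumulative-incidence estimator nor a competing-risk analysis is named anywhere in the protocol or its SAP section.

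**The concern.** Kaplan-Meier handles a censored subject as someone who could still have the event later. That is reasonable for a subject who moves away, but not for one who has died of cancer or sepsis. One minus Kaplan-Meier then estimates the risk in a hypothetical population in which nobody dies of non-CV causes. It exceeds the actual probability of CV death or HF hospitalization whenever some non-CV deaths precede a first event. The direction follows algebraically, whatever the non-CV death rate.

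What is at stake is the reading of the figure. Readers commonly take 12- or 24-month event probabilities, absolute risk reductions and numbers needed to treat from such curves. Under staggered entry, neither the crude proportion nor the patient-year rate gives the probability of an event by a fixed time, so the Kaplan-Meier curve is the only planned summary that appears to give it.

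**Working it through.** **The plan's own figures first.** Section 8.9 gives a placebo rate of 23% at 12 months for the composite and 11% for CV death, HR 0.80, a nominal one-sided level of 0.0242, 4872 subjects, 782 CV deaths for 80% power, and 1561 composite events for about 98% power. Without dilution, the Schoenfeld formula needs 4(1.973 + 0.842)²/(ln 0.80)² ≈ 637 events for 80% power, which does not match 782. The plan says it adjusts for dilution. A simulation used exponential hazards, 10% per year of vericiguat subjects reverting to the placebo hazard, 2% per year lost, 30 + 9 months and a 12-month ramp-up. With the accrual rate rising as the square of time, it gives 775 CV deaths (78.9% power) and 1549 composite events (97.8% power). With a linearly rising rate it gives 810 and 1610 events (80.6% and 98.2% power). The design figures are therefore reproduced closely, and constant hazards are a fair working model.

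**Inputs for the display check**
- Placebo composite hazard from section 8.9: λ = −ln(1 − 0.23) = 0.2614 per year.
- Vericiguat hazard, undiluted: 0.80 × 0.2614 = 0.2091 per year.
- Hazard of non-CV death before a first event, m: not in the documents, so assumed to be 0.01 to 0.04 per year. It cannot be derived from the cited trial of recently hospitalized patients, because section 4.1.1 gives its one-year mortality as 17% and section 8.9 gives its 12-month CV mortality as 17% too.

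**Formulas**
- One minus Kaplan-Meier: 1 − exp(−λt).
- Cumulative incidence: λ/(λ + m) × [1 − exp(−(λ + m)t)].

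**Worked example: placebo, 24 months, m = 0.04.** One minus Kaplan-Meier is 1 − exp(−0.5227) = 40.71%. Cumulative incidence is (0.2614/0.3014) × [1 − exp(−0.6027)] = 0.8673 × 0.4527 = 39.26%. The excess is 1.45 points.

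**Placebo arm** (excess computed before rounding)

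| Month | 1 − KM | Cumulative incidence, m = 0.01 | Cumulative incidence, m = 0.04 | Excess, points |
|---|---|---|---|---|
| 12 | 23.00% | 22.89% | 22.57% | 0.11 to 0.43 |
| 18 | 32.43% | 32.21% | 31.54% | 0.23 to 0.89 |
| 24 | 40.71% | 40.34% | 39.26% | 0.37 to 1.45 |
| 36 | 54.35% | 53.64% | 51.61% | 0.70 to 2.74 |

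In the vericiguat arm at 24 months, the figures are 34.18% against 33.86% to 32.94%, an excess of 0.32 to 1.24 points.

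**Difference between arms**

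| Month | By KM | m = 0.01 | m = 0.04 |
|---|---|---|---|
| 12 | 4.13 | 4.11 | 4.06 |
| 18 | 5.51 | 5.48 | 5.37 |
| 24 | 6.53 | 6.48 | 6.32 |

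The bias has the same sign and nearly the same size in each arm, so most of it cancels. The 24-month NNT is 1/0.0653 = 15.3 by Kaplan-Meier, against 1/0.0648 = 15.4 to 1/0.0632 = 15.8.

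**Wider range.** With m from 0.005 to 0.05 per year, the placebo excess at 18 months is 0.11 to 1.11 points.

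**The case against.** The strongest reply is that the effect is small and the plan already reports absolute measures without this bias. This largely stands. At 18 months, close to the planned median follow-up of 532 days, the placebo excess is below one point under the assumed 1% to 4% per year. Section 8.9 expects only 47% of subjects to reach 18 months, and the larger 36-month figures apply to very few in a 39-month trial with 30 months of accrual. Even with full follow-up of 2436 per arm, the 95% sampling error of the 24-month difference would be about ±2.7 points: 1.96 × √[(0.407 × 0.593 + 0.342 × 0.658)/2436]. A shift of 0.05 to 0.21 points is minor beside that. The plan also describes event-free survival curves; reading one minus the curve as risk is a step the reader takes.

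Four stronger inferences are tempting, and the documents do not support them.
- **The primary test is biased.** It is not. The log-rank test and Cox model compare cause-specific hazards, for which leaving the risk set at non-CV death is correct.
- **First HF hospitalization is displayed the same way, with a larger bias because CV death competes too.** The link in section 8.6.1 between secondary and primary analyses concerns the intention-to-treat principle. The only Kaplan-Meier sentence names the primary composite, and no curve is specified for the secondary endpoints.
- **The NNT of 22 in section 8.9 is inflated by this.** It is design arithmetic on assumed annual rates, 23% × 20% = 4.6 points, and comes from no curve. The Kaplan-Meier formula with the same inputs gives 4.13 points, an NNT of about 24.
- **The supportive analyses leave the matter uncovered.** They are deferred to a supplemental SAP that is not among the documents, so their content cannot be judged. Only the protocol's own silence on competing risks can be stated.

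The all-cause composite is free of competing death, but it is a different endpoint and does not correct this curve.

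**Conclusion.** The point holds as a minor reporting correction. Censoring at non-CV death combined with a Kaplan-Meier display makes one minus the curve an upward-biased estimate of the probability of CV death or HF hospitalization in both arms. The direction is certain if any non-CV death precedes a first event. The size rests on an assumed non-CV death rate, constant hazards and the plan's own 23% and HR 0.80: about 0.4 points or less at 12 months, and 0.4 to 1.5 points at 24 months in the placebo arm. The effect on the absolute difference at 24 months is about 0.2 points at most. No test, hazard ratio, alpha level, event count or power figure needs changing. Nor does the bias reach every absolute measure: the crude proportions and patient-year rates are free of it.

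**What to change.** Add one sentence to section 8.6.1: *Cumulative incidence by treatment group (Aalen-Johansen estimator, 95% CI) will be presented for the primary composite with non-CV death as a competing event.* State that any absolute risk, absolute risk reduction or NNT at a fixed time will be taken from this estimate.

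If curves are also shown for time to CV death or time to first HF hospitalization, use the same estimator, with non-CV death and death from any cause respectively as the competing event.

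Keep the stratified log-rank test and Cox model. Kaplan-Meier may stay as a companion display for the composite, and remains appropriate for all-cause mortality and for all-cause mortality or HF hospitalization, which have no competing death.

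The cost is one more standard analysis with no new data. The stated absolute risks and absolute reduction become slightly smaller.

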4.2.2 Rationale for Dose Selection/Regimen/Modification

Dose selection for Phase III is based on results from the Phase IIb study SOCRATES-REDUCED as well as the Phase I program in healthy volunteers.

Data from the Phase I studies show that in healthy volunteers doses up to 10 mg vericiguat are well tolerated. Dose limiting pharmacodynamics effects in Phase I studies at higher doses were associated with orthostatic reactions and syncope (see current version of IB).

In the Phase IIb SOCRATES-REDUCED study, vericiguat doses from 1.25 mg up to a target dose of 10 mg were tested. Vericiguat 1.25 mg was confirmed as a 'no effective dose' with an overall profile comparable to placebo. Vericiguat 2.5 mg was associated with a first dose SBP lowering effect of approximately 3 mmHg (minimally effective dose) and defined as the 'minimally effective dose'. Vericiguat 2.5 mg will be used as the starting dose for all subjects in Phase III. In the highest target dose arm, vericiguat was titrated from a starting dose of 2.5 mg by 2 dose doublings in 2-week intervals up to 10 mg target dose. The blood pressure criterion for up-titration was SBP \geq 100 mmHg. The target dose was reached by 72% of subjects receiving vericiguat compared to 75% of subjects sham up-titrated in the placebo group. The main reason for not up-titrating to target per protocol was maintaining dose without any increase when SBP was 90-100 mmHg. Dose decreases were rarely required for SBP <90 mmHg. 10 mg was safe and well tolerated with a clinically meaningful reduction in NT-proBNP and favorable trends in the impact on clinical events.

In conclusion, for vericiguat given on a background of standard of care, a titration regimen starting with 2.5 mg with blood pressure guided up-titration up to 10 mg once daily with 2 dose doublings about every 14 days is expected to cover doses from a minimal

hemodynamically effective starting dose to the maximum clinically favorable dose of 10 mg and is deemed appropriate for the planned Phase III study.

4.2.2.1 Rationale for the Use of Comparator/Placebo

As a novel mechanism, MK-1242 (vericiguat) is being developed for use on a background of standard of care rather than as a replacement for any established mechanisms. To allow a blinded assessment, vericiguat will be compared to a matching placebo. Utilizing placebo as a comparator to the novel sGC stimulator MK-1242 (vericiguat) allows for a representative population receiving standard of care under "real life" conditions.

4.2.3 Rationale for Endpoints

4.2.3.1 Efficacy Endpoints

The primary efficacy endpoint of the study is the time to first occurrence of the composite of CV death or HF hospitalization. As an integrated measure of HF morbidity and mortality, this endpoint integrates the cause-specific components CV death and HF hospitalization and is the most frequently used primary endpoint in recent phase III HFrEF trials. As secondary efficacy variables, the study will further assess the impact of MK-1242 (vericiguat) on the total number of HF hospitalizations further describing the impact on the patient journey and all cause death as an additional measure of net benefit.

4.2.3.2 Safety Endpoints

Safety assessments will include adverse events (AEs), physical examination findings, and vital signs including pulse rate and blood pressure assessment. Laboratory safety studies will include blood chemistry, hematology, and urine pregnancy testing (performed in women of childbearing potential). Additionally, 12-lead electrocardiograms will be performed.

AEs associated with symptomatic hypotension and syncope are pre-specified safety parameters and will be subject to inferential testing.

4.2.3.3 Pharmacokinetic Endpoints

Pharmacokinetic investigations will be performed to determine systemic exposure to MK-1242 (vericiguat) and its relationship with efficacy. Plasma concentrations of MK-1242 (vericiguat) will be collected at different time points using a sparse sampling approach in all participating subjects to facilitate this analysis.

4.2.3.4 Planned Exploratory Biomarker Research

Planned Genetic Analysis

Understanding genetic determinants of drug response is an important endeavor during medical research. This research will evaluate whether genetic variation within a clinical trial population correlates with response to the treatment(s) under evaluation. If genetic variation is found to predict efficacy or adverse events, the data might inform optimal use of therapies in the patient population. This research contributes to understanding genetic determinants of efficacy and safety associated with the treatments in this study.

4.2.3.5 Future Biomedical Research

The Sponsor will conduct Future Biomedical Research on DNA specimens collected for future biomedical research during this clinical trial.

Such research is for biomarker testing to address emergent questions not described elsewhere in the protocol (as part of the main trial) and will only be conducted on specimens from appropriately consented subjects. The objective of collecting specimens for Future Biomedical Research is to explore and identify biomarkers that inform the scientific understanding of diseases and/or their therapeutic treatments. The overarching goal is to use such information to develop safer, more effective drugs/vaccines, and/or to ensure that subjects receive the correct dose of the correct drug/vaccine at the correct time. The details of this Future Biomedical Research sub-trial are presented in Section 12.2 - Collection and Management of Specimens for Future Biomedical Research. Additional informational material for institutional review boards/ethics committees (IRBs/ERCs) and investigational site staff is provided in Section 12.3.

